13.3 Dose-Limiting Toxicities

Dose-limiting toxicities (DLTs) are any of the following drug related toxicities (any toxicities considered related, probably related, or possibly related to E7046) occurring during Cycle 1 as judged by the investigator.

- Nonhematologic toxicity \geq Grade 3 (except diarrhea, nausea and vomiting unless lasting >3 days despite optimal supportive care)
- Hematologic toxicity:
 - Grade 4 neutropenia for ≥ 5 days, or Grade 3 neutropenia with fever (fever is 38.4 °C),
 - Grade 4 thrombocytopenia, or Grade 3 thrombocytopenia with bleeding or lasting >7 days
- Any other toxicity assessed as related to E7046 treatment, and which in the opinion of a study investigator(s) the sponsor physician constitutes a dose-limiting toxicity
- Subjects who have missed > 4 days of dosing in Cycle 1 due to drug-related toxicity (but not qualifying for a DLT) will be assessed as experiencing a DLT.

Grading of toxicities is based on National Cancer Institute - Common Terminology Criteria for Adverse Events (NCI CTCAE) v4.03 (Section 13.4).

Adverse events occurring after Cycle 1 may be considered DLTs upon discussion between the investigator and the sponsor physician.

The following toxicities will not be considered DLTs:

- Grade 3 adverse event of tumor flare (defined as local pain, irritation, or rash localized at sites of known or suspected tumor)
- Grade 3 immune-related adverse event (irAE) that resolves to \leq Grade 1 within 7 days
 - An irAE, a subset of AEs, is defined as a clinically significant adverse event of any organ that is associated with study drug exposure, of unknown etiology, and is consistent with an immune-mediated mechanism. Serologic, immunologic, and

histologic (biopsy) data should be used to support an irAE diagnosis. Appropriate efforts should be made to rule out neoplastic, infectious, metabolic, toxin, or other etiologic causes of the irAE.

Subjects who do not complete at least 17 of 21 days of dosing in Cycle 1 due to reasons other than treatment related toxicity will be replaced for the purpose of DLT evaluation.

Assessment of DLTs will be discussed and agreed to by investigator(s) and sponsor physician prior to proceeding to the next dose level, and the decision will be documented.

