### Study Design

This is an open label, multicenter, Phase 1 study of E7046, a small molecule inhibitor of the prostaglandin E2 (PGE2) receptor type 4 (EP4). The study will be conducted in 2 parts: a dose escalation part to determine the MTD and/or RP2D of E7046, and a cohort expansion part with 6 to 16 subjects to better characterize safety, efficacy, pharmacokinetics (PK), and pharmacodynamics (PD) at the RP2D.

In the dose escalation part, increasing doses of E7046 will be administered to cohorts of 6 subjects, at dose levels ranging from 125 mg to 750 mg, (see Table below). In the first dose cohort, staggered dosing starts will be employed to ensure exposure of a limited number of subjects in initial dosing.

Dose level	No. of Subjects	E7046 Dose
-1	6	75 mg QD
1	6	125 mg QD
2	6	250 mg QD
3	6	500 mg QD
4	6	750 mg QD

Dose-limiting toxicities (DLTs) will be drug-related toxicities (considered related, probably related, or possibly related to E7046) and graded using NCI CTCAE 4.03 occurring during Cycle 1 and include:

- Nonhematologic toxicity  $\geq$  Grade 3 (except diarrhea, nausea and vomiting unless lasting  $>3$  days despite optimal supportive care)
- Confirmed (with a second measurement after 24 hours) nonhematologic appropriately-graded laboratory findings of Grade  $\geq 3$  that were  $\leq$  Grade 1 at baseline
- Hematologic toxicity: Grade 4 neutropenia  $\geq 5$  days, or Grade 3 neutropenia with fever, Grade 4 thrombocytopenia, or Grade 3 thrombocytopenia with bleeding or lasting  $>7$  days
- Any other toxicity assessed as related to E7046 treatment, and which, in the opinion of the study investigator(s) and the sponsor physician constitutes a dose-limiting toxicity
- Missed  $\geq 7$  days of dosing in Cycle 1 due to drug-related toxicity (but not qualifying for a DLT).

The following toxicities will not be considered DLTs:

- Grade  $\leq 3$  adverse event of tumor flare (defined as local pain, irritation, or rash localized at sites of known or suspected tumor)
- Grade  $\leq 3$  immune-related adverse event (irAE) that resolves to Grade  $\leq 1$  within 7 days (see protocol body for definition of irAE)

Subjects who for reasons other than drug related toxicity or a DLT, fail to complete 75% of the planned total dose in Cycle 1, (equivalent to 16 out of 21 days) will be replaced.

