**Table 1 Dose Cohorts in E7046 Dose-Escalation**

Dose level	No. of Subjects	E7046 Dose
-1	6	75 mg QD
1	6	125 mg QD
2	6	250 mg QD
3	6	500 mg QD
4	6	750 mg QD

QD = once daily.

The schema for dose escalation is adopted and modified from the traditional 3+3 design and is shown in [Figure 3](#). Dose limiting toxicities are defined in [Section 9.1.1.2](#).

Enrollment for first dose cohort (125 mg QD): (see Figure 3 Panel B)

In the first cohort, staggered dosing will be employed as described below.

Suspected severe immune reactions (ssIR) are defined as listed in the CTCAE v4.03 "Immune System Disorders", including Allergic Reaction, Anaphylaxis, and Cytokine Release Syndrome.

*First 3 subjects (Subjects 1, 2, and 3)*

- Initially one subject (Subject #1) will be enrolled and dosed.
  - If after 14 days of dosing no suspected severe immune reactions are observed, another 2 subjects (Subjects # 2 and 3) will be enrolled and dosed.
  - If within the first 14 days, Subject #1 experiences a suspected severe immune reaction, another subject (Subject #2) will be enrolled and dosed.
    - If after 14 days of dosing no suspected severe immune reactions are observed for Subject #2, another subject (Subject #3) will be enrolled and dosed.
    - If within the first 14 days, Subject #2 also experiences a suspected severe immune reaction, enrollment in this dose cohort will stop. A lower dose level of 75 mg QD (Dose Level -1) may be tested. Enrollment of the 6 subjects at Dose Level -1 will follow the same staggered schema as described for Dose Level 1.

*Next 3 subjects (Subjects 4, 5, and 6)*

- After evaluation of the first 3 subjects for DLTs after 21 days (Cycle 1), enrollment will continue as follows:
  - If  $\leq 1$  of 3 first subjects experiences DLTs in Cycle 1, the remaining 3 subjects (Subjects # 4, 5, and 6) in the first cohort will be enrolled and treated.
  - If  $>1$  of 3 first subjects experiences DLTs in Cycle 1, a lower dose level of 75 mg (dose level -1) will be tested, following the same enrollment schema as described for Dose Level 1.

Enrollment of subsequent dose cohorts:

[figure not shown]
- There will be no staggered dosing after the first dose cohort, however the subject enrolment will be controlled so that no more than one subject will be dosed on the same day.
- If  $\geq 2$  of 6 subjects in any dose cohort experiences a DLT, then dose escalation will be stopped.

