- If  $\leq 1$  of 6 subjects in a dose cohort experiences a DLT, then 6 subjects will be enrolled at the next higher dose level. Dose escalation will continue until a dose level is reached where  $\geq 2$  subjects experience a DLT, or when 750 mg is reached based on

an integrated evaluation of safety, tolerability, clinical benefit, PK, and pharmacodynamic data, for all dose levels tested.

[figure not shown]
Additional enrollment (if necessary)

If needed for selection of RP2D, an additional 3 subjects may be enrolled at 1 or 2 selected dose levels.

Panel A: Overall Dose Escalation Schema

Panel B: First Dose Cohort (Staggered dosing)

ssIR = suspected severe immune reaction

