**Figure 3      Schema for Dose Escalation**

### 9.1.1.2 Dose-Limiting Toxicities

Dose-limiting toxicities (DLTs) are any of the following drug related toxicities (any toxicities considered related, probably related, or possibly related to E7046) occurring during Cycle 1 as judged by the investigator.

- Nonhematologic toxicity  $\geq$  Grade 3 (except diarrhea, nausea and vomiting unless lasting  $>3$  days despite optimal supportive care)
- Confirmed (with a second measurement after 24 hours) nonhematologic appropriately-graded laboratory findings of Grade  $\geq 3$  that were  $\leq$  Grade 1 at baseline
- Hematologic toxicity:
  - Grade 4 neutropenia for  $\geq 5$  days, or Grade 3 neutropenia with fever (fever is  $38.4^{\circ}\text{C}$ ),
  - Grade 4 thrombocytopenia, or Grade 3 thrombocytopenia with bleeding or lasting  $>7$  days
- Any other toxicity assessed as related to E7046 treatment, and which in the opinion of the study investigator(s) and the sponsor physician constitutes a dose-limiting toxicity
- Subjects who have missed  $\geq 7$  days of dosing in Cycle 1 due to drug-related toxicity (but not qualifying for a DLT) will be assessed as experiencing a DLT.

Grading of toxicities is based on National Cancer Institute - Common Terminology Criteria for Adverse Events (NCI CTCAE) v4.03 ([Appendix 4](#)).

Adverse events occurring after Cycle 1 may be considered DLTs upon discussion between the investigator(s) and the sponsor physician.

The following toxicities will not be considered DLTs:

- Grade  $\leq 3$  adverse event of tumor flare (defined as local pain, irritation, or rash localized at sites of known or suspected tumor)
- Grade  $\leq 3$  immune-related adverse event (irAE) that resolves to Grade 1 or less within 7 days, while not constituting a DLT for dose escalation purposes, may preclude further administration of study drug or study drug may be continued at a reduced dose after discussion and agreement with Eisai medical monitor.
  - An irAE, a subset of AEs, is defined as a clinically significant adverse event of any organ that is associated with study drug exposure, of unknown etiology, and is consistent with an immune-mediated mechanism. Serologic, immunologic, and histologic (biopsy) data should be used to support an irAE diagnosis. Appropriate efforts should be made to rule out neoplastic, infectious, metabolic, toxin, or other etiologic causes of the irAE.

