Subjects who for reasons other than drug related toxicity or a DLT, fail to complete 75% of the planned total dose in Cycle 1, (equivalent to 16 out of 21 days) will be replaced.

Assessment of DLTs will be discussed and agreed to by investigator(s) and sponsor physician prior to proceeding to the next dose level, and the decision will be documented.

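### SAP 13.3 does not match the protocol's DLT and replacement criteria, so the SAP's DLT status and DLT Evaluable Set can contradict the escalation decisions

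*SAP*

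**What the plan says.** **Missed dosing for drug-related toxicity.** In protocol 9.1.1.2 the trigger is 7 or more "days of dosing in Cycle 1 due to drug-related toxicity (but not qualifying for a DLT) will be assessed as experiencing a DLT". The synopsis gives the same limit. SAP 13.3 counts "Subjects who have missed > 4 days of dosing in Cycle 1 due to drug-related toxicity".

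**Replacement for reasons other than toxicity.** Protocol 9.1.1.2 says that subjects who "fail to complete 75% of the planned total dose in Cycle 1, (equivalent to 16 out of 21 days) will be replaced". SAP 13.3 instead replaces, for the purpose of DLT evaluation, "Subjects who do not complete at least 17 of 21 days of dosing in Cycle 1".

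**Laboratory findings.** Protocol 9.1.1.2 lists a separate DLT item for confirmed nonhematologic laboratory findings of Grade 3 or higher that were Grade 1 or lower at baseline. SAP 13.3 has no such item.

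**Where 13.3 is used.** SAP 5.2.1 defines the DLT Evaluable Set by reference to 13.3. SAP 5.6.2 cites 13.3 when describing how each subject's DLT status and reasons are determined, and says the result will be listed. The protocol's own definition of this set (9.7.1.2) points to 9.1.1.2.

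**What rests on the DLT count.** Under protocol 9.1.1.1, if 2 or more "of 6 subjects in any dose cohort experiences a DLT, then dose escalation will be stopped"; if 1 or fewer "of 6 subjects in a dose cohort experiences a DLT, then 6 subjects will be enrolled at the next higher dose level". The MTD is one level below the level with 2 or more DLTs in 6 (9.1.1.3), and the RP2D may not exceed it (9.1.1.4). Protocol 9.7.1.6 says the MTD follows the protocol definition.

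**Versions.** SAP Section 3 names Amendment 01 of 30 December 2015. SAP Section 7 names v1.0 of 7 May 2015 and states that no changes to the planned analysis apply.

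**The concern.** DLT status is the event behind the MTD part of the primary endpoint, and the decision turns on a single subject: 1 of 6 escalates and 2 of 6 stops. Two documents that describe the same determination should use the same criteria. Here they do not, and the SAP does not acknowledge the difference.

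Two things are at stake. The first follows from the text: a SAP listing and evaluable set that disagree with the documented escalation decisions, with nothing in the SAP to explain why. The second is conditional: if the team reviewing a cohort used 13.3 instead of 9.1.1.2, escalation could stop earlier and the MTD could be lower than the protocol's rule would give.

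**Working it through.** **Step 1. The protocol's day conversion.** 0.75 × 21 = 15.75, so a subject taking full doses needs 16 days. This reproduces the protocol's stated equivalence. As proportions, 16/21 = 76.2% and 17/21 = 81.0%. The SAP's two limits agree with each other: 21 − 4 = 17.

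**Step 2. Where the rules disagree.** Subjects on full daily doses:

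| Days missed | Days dosed | DLT if missed for toxicity: protocol / SAP | Replaced if missed for other reasons: protocol / SAP |
|---|---|---|---|
| 4 | 17 | no / no | no / no |
| 5 | 16 | no / **yes** | no / **yes** |
| 6 | 15 | no / **yes** | yes / yes |
| 7 | 14 | yes / yes | yes / yes |

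The DLT rules part at 5 and 6 missed days. The protocol does not replace that subject either, because the reason is toxicity, so he or she remains an evaluable non-DLT. With full doses, the replacement rules part at exactly 16 days. The protocol rule is on total dose and the SAP rule on days, so they can also part elsewhere: a subject dosed on 17 or more days with partial doses for non-toxicity reasons could fail the protocol rule and pass the SAP rule.

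**Step 3. Effect on a cohort, if 13.3 were applied at the review.** With the planned dose levels:

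- 500 mg: 1/6 escalates to 750 mg; 2/6 stops, with an MTD of 250 mg.
- 750 mg, with no more than 1/6 at any level: MTD not reached. At 2/6: MTD 500 mg, and the RP2D is capped there.

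**Step 4. How often.** The documents give no rate, so both inputs are assumptions: p is the risk of a protocol DLT, and q is the risk of missing 5 or 6 days for toxicity with no other DLT. For six independent subjects,

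P(≥2 of 6; r) = 1 − (1 − r)^6 − 6r(1 − r)^5,

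with r = p under the protocol and r = p + q under 13.3.

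| p | q | Protocol | SAP 13.3 | Rise (points) |
|---|---|---|---|---|
| 0.05 | 0.01 | 0.0328 | 0.0459 | 1.3 |
| 0.10 | 0.02 | 0.1143 | 0.1556 | 4.1 |
| 0.10 | 0.05 | 0.1143 | 0.2235 | 10.9 |

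The rise is taken before rounding.

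**Step 5. The same effect in a cohort that already has exactly one protocol DLT.** The chance that at least one of the other five is affected is 1 − (1 − q/(1 − p))^5. At p = 0.05, q = 0.01 it is 0.0515; at p = 0.10, q = 0.02 it is 0.1063. These look larger only because they condition on a cohort at the boundary.

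**Step 6. Allowing for discretion.** The protocol also counts any other related toxicity that "in the opinion of the study investigator(s) and the sponsor physician constitutes a dose-limiting toxicity". If half of the affected subjects would be called DLTs on that ground anyway, the protocol rate becomes p + q/2. At p = 0.10, q = 0.02, P(≥2 of 6) goes from 0.1345 to 0.1556, a rise of 2.1 points instead of 4.1.

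**The case against.** The strongest reply is that the documents already say which definition prevails. Protocol 9.7.1.6 determines the MTD by the protocol definition, protocol 11.2 binds investigators to the protocol, and the SAP contains no MTD rule. Escalation decisions are agreed and documented before each next dose level, whereas the SAP need only be final before database lock. SAP 5.6.2 mentions 13.3 in a parenthesis after the word for reasons, which can be read as a pointer to reason categories and not as an order to set the protocol aside. It also says that the status determined at the team's review is what gets listed.

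This largely stands. A reader might infer from the two texts that the MTD has two governing definitions, or that escalation is compromised. The documents do not support either reading: if reviewers follow the protocol, the effect on escalation is zero.

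It does not remove the inconsistency. SAP 5.2.1 still builds the DLT Evaluable Set from 13.3, and 13.3 is the only set of criteria that 5.6.2 cites. The discretionary clause softens the difference but cannot reconcile two fixed thresholds.

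Two limits apply to the finer points. That a subject with 16 dosing days leaves the evaluable set, making it 5 instead of 6 if unreplaced, is an inference from the replacement wording, since SAP 5.2.1 does not spell out exclusion. And the missing laboratory item need not mean such findings are lost: the general nonhematologic item in 13.3 might still capture them, without the confirmation and baseline conditions.

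**Conclusion.** The mismatch is real and should be fixed. The firm conclusion is that SAP 13.3 is wrong as written against the supplied protocol on the missed-dose limit, the replacement limit and the laboratory item. The SAP can therefore classify a subject with 5 or 6 toxicity-related missed days as a DLT, and can treat a subject with full doses on exactly 16 days for other reasons as not evaluable, in conflict with the decisions taken during escalation.

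A changed MTD is a conditional consequence, arising only if reviewers apply 13.3. Its size rests on assumed rates: about 1.3 points in P(≥2 of 6) at p = 0.05, q = 0.01 and 4.1 points at p = 0.10, q = 0.02, per cohort, treating subjects as independent and ignoring discretionary calls. The protocol itself expects that an MTD may not be reached, with the RP2D then chosen on integrated evidence.

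A reader might also infer that 13.3 was carried over from an older protocol version, given the two versions cited. That is plausible but cannot be confirmed, because the version of the supplied protocol is not visible. No view is taken on which SAP citation is correct.

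**What to change.** Before database lock:

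1. Replace the criteria in SAP 13.3 with the DLT and replacement criteria of the protocol version used for the escalation decisions. In the supplied protocol these are 7 or more missed days, 75% of the planned total dose (16 of 21 days), and the confirmed laboratory item. Copy the section whole, since the exemptions for tumor flare and immune-related events also differ (Grade 3 in the SAP, Grade 3 or lower in the protocol).
2. Define the DLT Evaluable Set in SAP 5.2.1 from that same section, and say whether replaced subjects are excluded.
3. State in SAP 5.6.2 that the listed DLT status is the one agreed at the escalation review under those criteria.
4. Cite one protocol version in SAP Sections 3 and 7.

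The cost is SAP wording only. No new data are needed and conduct of the trial does not change.

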#### 9.4.1.1 Dose modifications

Toxicity will be managed by concomitant medication (as appropriate), treatment interruption, dose reduction and treatment discontinuation, or a combination of these.

Dose reduction is allowed for all subjects during all cycles of treatment.

Subjects who experience a DLT in Cycle 1 may be allowed to continue study drug at a reduced dose after discussion with sponsor Medical monitor if this is judged to be in their best interest (see dose modification guidelines below).

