5.2 STUDY SUBJECTS

5.2.1 Definitions of Analysis Sets

Full Analysis Set will include all subjects who received at least one dose of study drug. This will be the primary analysis set for efficacy evaluations, as well as for demographic and baseline characteristics. This analysis set will also constitute the **Safety Analysis Set**.

DLT Evaluable Set will consist of those subjects who are evaluable for the DLTs (Section 13.3). This will be the analysis set for DLT analysis.

Pharmacokinetic (PK) Analysis Set will include all subjects who have received at least one dose of study drug and have at least one evaluable plasma concentration.

Pharmacodynamic (PD) Analysis Set will include all subjects who have received at least 1 dose of study drug and have evaluable pharmacodynamic data.

Pharmacokinetic/Pharmacodynamic (PK/PD) Analysis Set will consist of all subjects in the Safety Analysis Set that also have evaluable serum PK and PD pretreatment assessment and at least 1 post treatment assessment.

Response Evaluable Set will consist of those subjects who have received at least 1 dose of study drug and have measurable disease at baseline and at least 1 post-baseline evaluation. This will be the primary analysis set for tumor response analysis.

FDG-PET Analysis Set will include all subjects with a baseline and at least one post baseline evaluable FDG-PET/CT assessment.

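### SAP 13.3 replaces under-dosed subjects with no exception for a DLT already observed, so read literally that DLT can drop out of the DLT analysis set

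*SAP*

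**What the plan says.** SAP 13.3 sets the replacement rule. "Subjects who do not complete at least 17 of 21 days of dosing in Cycle 1" and whose shortfall is "due to reasons other than treatment related toxicity will be replaced for the purpose of DLT evaluation". The sentence has two conditions, days dosed and reason for the shortfall. DLT status is not one of them.

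Protocol 9.1.1.2 and the synopsis carry a similar rule, for those who "for reasons other than drug related toxicity or a DLT, fail to complete 75% of the planned total dose", which they equate to 16 of 21 days. The protocol therefore names a DLT among the excluded reasons, which the SAP does not, and it uses a different threshold.

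SAP 5.2.1 says the DLT Evaluable Set "will consist of those subjects who are evaluable for the DLTs (Section 13.3"), and makes it the set for DLT analysis. Section 13.3 contains no other dosing or evaluability criterion.

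Two further passages matter. Protocol 9.4.1.1 says: "Subjects who experience a DLT in Cycle 1 may be allowed to continue study drug at a reduced dose". Protocol 9.1.1.1 says that if two or more of 6 "subjects in any dose cohort experiences a DLT, then dose escalation will be stopped"; 9.1.1.3 defines the MTD from the same 2-of-6 criterion.

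**The concern.** An observed DLT is complete information: no further dosing is needed to classify that subject. Only a DLT-free subject with too little dosing is uninformative. The SAP sentence does not separate the two.

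The case can arise. A subject has a DLT on Day 6, resumes at a reduced dose, and stops on Day 12 for clinical progression or withdrawal of consent. Fewer than 17 days have been dosed and the recorded reason for stopping is not toxicity, so the sentence calls for replacement. Protocol 9.5.9 records one primary reason for leaving the study and lists adverse events, subject choice and withdrawal of consent separately, so a departure soon after a DLT can be recorded under a non-toxicity reason.

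The protocol wording is only partly protective. Its mention of a DLT qualifies the reason for not completing, so it does not clearly retain a subject whose DLT came first and whose stopping had another recorded cause.

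The MTD is a primary endpoint and the decision turns on one subject: 2 of 6 stops escalation, 1 of 6 does not.

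**Working it through.** **Thresholds.** The protocol figure reproduces: 0.75 × 21 = 15.75, rounded up to 16 days. The SAP requires 17 days (17/21 = 81%, against 16/21 = 76%). A subject dosed on exactly 16 days, short for a non-toxicity reason, is replaced under the SAP and kept under the protocol.

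**Direct case.** Two DLTs occur among 6 subjects; one of the two later stops for another reason before Day 17.
- DLT retained: 2/6.
- Literal SAP rule: 1 DLT among 5, plus a replacement. If the replacement is DLT-free the count is 1/6, although 2 of 7 treated subjects (29%) had a DLT.

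**Illustration.** The documents give no true DLT rate and no replacement rates, so all three inputs are assumptions: p = true DLT rate; d = share of DLT subjects replaced; d0 = share of DLT-free subjects replaced.

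DLT rate among counted subjects under the literal rule: p(1−d) / [p(1−d) + (1−p)(1−d0)].

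Chance of at most 1 DLT in 6 at rate x: (1−x)^6 + 6x(1−x)^5.

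With p = 1/3:

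| Case | Counted DLT rate | P(≤1 of 6) |
|---|---|---|
| True rate | 0.333 | 0.351 |
| d = 10%, d0 = 10% | 0.333 | 0.351 |
| d = 20%, d0 = 10% | 0.2667/0.8667 = 0.308 | 0.404 |
| d = 30%, d0 = 10% | 0.2333/0.8333 = 0.280 | 0.464 |

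The differences from the true rate are 0.404 − 0.351 = 0.053 and 0.464 − 0.351 = 0.113. When d = d0 the factors cancel and the counted rate equals p, so the literal rule then causes no bias.

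**Other rates.** With d0 = 0 and p from 0.20 to 0.50, the chance of stopping at a dose (2 or more of 6) falls by about 1 to 2 points at d = 5%, 3 to 5 at d = 10%, 6 to 10 at d = 20% and 11 to 16 at d = 30%. For p = 0.33 and d = 20% it falls from 0.642 to 0.542.

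**Effect of retaining every DLT.** With d0 = 10%, keeping all DLT subjects and replacing only DLT-free ones gives a counted rate of 0.3333/(0.3333 + 0.6) = 0.357 and P(≤1 of 6) = 0.306. That is above the assumed true rate, so 0.306 is not the benchmark for bias.

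**The case against.** The strongest reply is that loss of the DLT is an inference. No sentence says a replaced subject's DLT is disregarded; replacement says only that another subject is enrolled. The DLT Evaluable Set refers to the whole of SAP 13.3, which opens with the definition of a Cycle 1 DLT, so a subject meeting that definition can be read as evaluable.

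The decision rules also do not mention that set. Protocol 9.1.1.1 states in one place that escalation runs until two or more subjects at a dose have a DLT, with no denominator. In the direct case that wording stops escalation. Protocol 9.7.1.6 determines the MTD by the protocol definition. SAP 5.6.2 determines and lists DLT status for each subject, the event stays in the safety tables, and both documents require documented agreement on DLTs by investigators and sponsor before the next dose level.

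The route is narrow too. Under protocol Table 2, Grade 3 related toxicity leads to interruption and Grade 4 mostly to discontinuation, so most days missed after a DLT would be attributed to toxicity and would not trigger replacement. The first scheduled scan is at Week 6, after Cycle 1 ends, so progression within Cycle 1 would have to be clinical or found on an earlier scan.

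All of this stands as a limit on the consequence. It does not cure the sentence, which says such a subject will be replaced for DLT evaluation, and no passage says that an observed DLT keeps its subject in the count.

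**Conclusion.** Wrong as written; it should be fixed. SAP 13.3 and 5.2.1, followed literally, allow an observed Cycle 1 DLT to leave the analysis set and the 2-of-6 count for a primary endpoint.

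A reader might infer that the plan directs escalation past a dose with two DLTs. The documents do not support that: the no-denominator wording in protocol 9.1.1.1, the per-subject determination and the documented review all point towards keeping the DLT. A reader might also infer that DLT rates will be biased downward, or set 0.404 against 0.306 as the size of the effect. The downward bias needs DLT subjects to be replaced more often than DLT-free subjects. That is plausible if withdrawal follows a DLT, but the documents give no rate for it. Of the 0.404 to 0.306 gap (0.098), 0.053 comes from the literal rule and 0.045 from a comparator that lies above the assumed true rate.

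Under the stated assumptions (true rate 1/3, 10% of DLT-free subjects replaced), the chance of at most 1 of 6 rises from 0.351 to 0.404 or 0.464 when 20% or 30% of DLT subjects are replaced, and not at all at 10%. The gap in the wording does not depend on these rates.

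**What to change.** 1. SAP 5.2.1: define the DLT Evaluable Set as subjects who had a Cycle 1 DLT or who met the minimum Cycle 1 dosing. Align the protocol's set definition in 9.7.1.2.
2. SAP 13.3, protocol 9.1.1.2 and the synopsis: limit replacement to subjects without an observed DLT who fall short of the minimum dosing for reasons other than treatment-related toxicity, and say that a subject with an observed Cycle 1 DLT stays DLT-evaluable whatever the number of days dosed.
3. Reconcile the two documents on the mention of a DLT among the excluded reasons and on the threshold (17 versus 16 of 21 days). This review does not choose the threshold. SAP section 3 cites Amendment 01 and section 7 cites protocol v1.0, so the SAP should also state which version it follows.
4. Reconcile the two statements of the escalation rule in protocol 9.1.1.1, with and without the denominator of 6.

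The cost is a few sentences in the SAP and a matching protocol clarification. No extra subjects are needed, and there may be slightly fewer replacements.
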